The screening visit will occur 8-16 weeks prior to start of rIL-2 treatment, and will include:

- History and complete physical examination that includes evaluation of adequate venous access for leukapheresis
- Height and weight measurements
- Concomitant medication review
- CBC and metabolic panel
- Pregnancy test
- Thyroid function tests and anti-Tpo antibodies
- CD4+ and CD8+ T cell count (both absolute and as percent of lymphocytes).
- Plasma HIV RNA level (using the locally available assay) and verification that plasma HIV RNA levels prior to screening meet the inclusion criteria.
- Hepatitis B and C testing
- Informed consent

D.2.2. Leukapheresis Visit

The pre-treatment leukapheresis visit will occur 4-8 weeks prior to start of rIL-2 treatment, and will include:

- Interval history and targeted physical examination
- Concomitant medication review.
- CBC and metabolic panel
- CD4+ and CD8+ T cell count (both absolute and as percent of lymphocytes) and documentation of all interim CD4+ counts (absolute and percents).
- Thyroid function tests and anti-Tpo antibodies.
- Participant will be instructed as to how IL-2 will be injected subcutaneously. Instructions for preparing rIL-2 for administration are given in the Manual of Operations, which includes the Investigator's Brochure as an appendix. Participants receiving rIL-2 will be taught to give themselves injections. Participants will be given a dosing log for future use and will be encouraged to refer to it during their daily activities. Supporting materials for clinical staff and for participants on administering rIL-2 and managing expected side effects are included in the Manual of Operations. The Manual of Operations also includes contact information for questions concerning clinical management. No rIL-2 will be administered at this visit.
- A 4 liter leukapheresis will be performed at the Seidman Ambulatory Stem Cell Transplant

Unit at University Hospitals using AIDS protocol 328.

- Plasma will be frozen for single copy HIV RNA assay.
- Leukapheresis samples will be processed into PBMC that will be cryopreserved for assays of:
 - HIV reservoir by QVOA
 - HIV reservoir by EDITS
 - Total and intact proviral DNA assay (Accelavir)
 - Immune Cell Phenotype
 - NK cell phenotype

D.2.3. rIL-2 Initial Treatment Visit – Cycle 1, Day 0

The first IL-2 cycle will start 4-8 weeks after the leukapheresis visit and will include:

- Interval history and targeted physical examination, including weight.

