Staff will contact the participant by phone to assess tolerance and compliance with injection schedule

D.2.10. End of Study Visit (or Premature Discontinuation Visit)

NOTE: The end of study visit should take place 8 weeks (+/- 2 weeks) after Day 0 of the last (8th) treatment cycle. In the case of premature discontinuation, the end of study visit should take place at least 6 weeks after day 0 of the last treatment cycle and may take place up to 10 weeks after day 0 of the last treatment cycle.

These visits will include:

- Interval history and targeted physical examination.
- Immunogenicity testing
- CD4+ and CD8+ T cell count (both absolute and as percent of lymphocytes)
- Plasma HIV RNA level by PCR (using the locally available assay)
- IL-2 immunogenicity
- At this visit the participant will undergo a 4 Liter leukapheresis at the Seidman Ambulatory Stem Cell Transplant Unit at University Hospitals using AIDS protocol 328.
- Plasma will be cryopreserved for single copy HIV RNA assay
- Leukapheresis product PBMC will be cryopreserved for:
 - HIV reservoir assay by EDITS
 - HIV reservoir assay by QVOA
 - Total and intact proviral DNA assay (Accelavir)
 - Assays of immune cell phenotype and NK cell phenotype

If leukapheresis cannot be done after premature treatment discontinuation for any reason, a 120 cc. blood draw will be obtained for preparation of PBMC and plasma. Based upon cell yield these samples will be used for:

- Plasma will be cryopreserved for single copy HIV RNA assay
- HIV reservoir assay by EDITS
- HIV reservoir assay by QVOA
- Total and intact proviral DNA assay (Accelavir)
- Assays of immune cell phenotype and NK cell phenotype

D.2.11. Immunogenicity follow-up

Participants who have detectable neutralizing antibodies at the end of study visit will be followed approximately every 90 days for repeat testing until 12 months after the end of study or until a negative result is obtained. During these visits, an interval medical history and targeted physical exam will be conducted. If clinically significant events have occurred, the participant will be referred for appropriate medical care.

D.2.12. Management of off-window visits

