All adverse events grade 2 or greater will be reviewed in real time by the study investigators, who will establish their relationship to study treatment (see below). The study investigators will also determine whether specific treatment for each adverse event is warranted, whether they meet criteria for study treatment discontinuation, and whether they constitute an emerging exclusionary criterion.

In addition to the real-time review of adverse events, the study data manager and statistician will prepare a bi-yearly report of accrual, early study treatment and study discontinuations (and related reasons), baseline characteristics, longitudinal CD4 T cell count and plasma HIV RNA measurements, Grade ≥ 2 signs and symptoms, Grade ≥ 2 laboratory abnormalities and reported serious adverse events (SAEs). This report will be reviewed by the research team and the Safety Monitoring Committee (SMC) during regularly scheduled conference calls every 6 months. The investigators and SMC chair may jointly forgo an actual conference call if the reports have been reviewed and no additional discussion is deemed necessary.

In addition to the regularly scheduled reviews, the SMC will perform expedited reviews of the safety data whenever any of the following happens:

- Two or more participants have experienced a grade 4 AE that is deemed possibly, probably, or definitely related to study treatment
- Any death occurs on study that is deemed possibly, probably, or definitely related to study treatment

Whenever either of the two criteria immediately above occurs, enrollment into the study will be paused until the SMC review has taken place and a determination has been made that enrollment can resume.

The SMC will be composed of an investigator affiliated with Case Western Reserve University in a department other than the Division of Infectious Diseases and HIV Medicine, an investigator not affiliated with Case Western Reserve University, and a biostatistician with no direct responsibilities managing trial-derived data.

H. DATA COLLECTION AND MONITORING AND ADVERSE EVENT REPORTING

H.1. RECORDS TO BE KEPT

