Important medical events that may not result in death, are not life-threatening, and do not require hospitalization may be considered serious when, based upon appropriate medical judgment, they may jeopardize the patient or subject and may require medical or surgical intervention to prevent one of the outcomes listed in this definition. Examples of such medical events include allergic bronchospasm requiring intensive treatment in an emergency room or at home, blood dyscrasias or convulsions that do not result in inpatient hospitalization, or the development of drug dependency or drug abuse.

H.3.1.6. Life-Threatening

An adverse event or suspected adverse reaction is considered *life-threatening* if, in the view of the investigators, its occurrence places the patient or subject at immediate risk of death. It does not include an adverse event or suspected adverse reaction that, had it hypothetically occurred in a more severe form, might have caused death.

H.3.2. Expedited Adverse Event Reporting

If a death occurs during the treatment phase of the study or within 30 days after the last administration of the study drug(s) and it is determined to be related either to the study drug(s) or to a study procedure, the investigators or his/her designee must notify the SMC Chair (or qualified alternate) no later than 3 reporting days after the investigators become aware of the event. For the purposes of expedited reporting to the SMC the definition of a “reporting day” in Version 2.0 of the DAIDS EAE Manual will be used, i.e, a reporting day begins at 12:00 AM and ends at 11:59 PM local time, Monday through Friday, holidays falling from Monday through Friday included.

H.3.3. Reporting to the University Hospitals of Cleveland Medical Center (UHCMC) Institutional Review Board (IRB)

In compliance with the UHCMC IRB policy titled “Event Reporting – Unanticipated Problems, Adverse Events, and Protocol Deviations”, the Principal Investigators will report all non-fatal events meeting the UHCMC IRB definition of *unanticipated problem involving risk to participants or others* within 14 calendar days of awareness of the event. All fatal events will be reported to the IRB within 7 calendar days of awareness of the event.

H.3.4. Expedited Reporting to the Food and Drug Administration

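### The 3-day SMC notice for procedure-related deaths (H.3.2) misses any death from the final leukapheresis and any pre-dosing death from the baseline one

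*Combined protocol and SAP*

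**What the plan says.** All references are to the combined protocol and SAP.

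- **H.3.2, scope.** The rule applies to a death "related either to the study drug(s) or to a study procedure".
- **H.3.2, window.** "If a death occurs during the treatment phase of the study or within 30 days after the last administration of the study drug(s").
- **H.3.2, deadline.** The SMC Chair is to be notified "no later than 3 reporting days after the investigators become aware of the event".
- **D.2.2, baseline procedure.** "The pre-treatment leukapheresis visit will occur 4-8 weeks prior to start of rIL-2 treatment". The section adds: "No rIL-2 will be administered at this visit".
- **D.2.10, final procedure.** "The end of study visit should take place 8 weeks (+/- 2 weeks) after Day 0 of the last (8th) treatment cycle". The second 4-litre leukapheresis is done at this visit. After premature discontinuation the visit falls 6 to 10 weeks after Day 0 of the last cycle given.
- **G and I.3, death trigger.** Expedited SMC review and an enrolment pause follow if "Any death occurs on study that is deemed possibly, probably, or definitely related to study treatment". Procedures are not mentioned.
- **Other routes.** H.3.3 sends every death to the IRB within 7 calendar days. H.3.9 sends adverse events of grade 3 and above to the SMC and FDA and gives no number of days. H.3.8 sets the expedited reporting period as the whole of a participant's time on study.

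**The concern.** H.3.2 names procedure-related deaths as part of its scope but fixes its window by drug dosing alone. Apart from the two leukaphereses, the study procedures are blood draws and subcutaneous injections, so a reader would expect the rule to cover the leukaphereses first of all. One is scheduled before dosing starts and the other well after it ends.

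The two procedures are about 59 to 88 weeks apart for a participant who completes all cycles: 4–8 weeks to cycle 1, seven intervals of 7–10 weeks, then 6–10 weeks to the final visit (4 + 49 + 6 = 59; 8 + 70 + 10 = 88). When a procedure-related death occurred, other participants could still be facing the same procedure. The SMC is the body that would advise on whether to go on, and the protocol gives it no timed notice of that death and no automatic review.

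**Working it through.** H.3.2 states its 30 days as a rule, so there is no derived figure to reproduce. The check is calendar arithmetic on the protocol's own visit windows. Day 0 below is Day 0 of the last cycle.

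**Inputs**
- Cycle: twice-daily doses on 4 consecutive days, Day 0 to Day 3 (C.1, C.5.1.1), so the last dose is on Day 3.
- Tail of the window: 30 days after the last dose (H.3.2).
- Final leukapheresis: 8 ± 2 weeks, so Day 42 to 70, target Day 56 (D.2.10).
- Baseline leukapheresis: 4–8 weeks, so 28 to 56 days before the first dose (D.2.2).

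**Final leukapheresis**
- Window closes: 3 + 30 = Day 33.
- Gap: 42 − 33 = 9 days at the earliest, 56 − 33 = 23 at target, 70 − 33 = 37 at the latest.
- A death from this procedure cannot come before it, so every such death falls after the window has closed.

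**Sensitivity to the day of the last dose** (last dose = (number of doses − 1) × interval ÷ 24 h)

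| Case | Last dose | Window closes | Gap to Day 42–70 |
|---|---|---|---|
| 4-day cycle, as above | Day 3 | Day 33 | 9 to 37 days |
| 8 doses at the maximum 18 h spacing (C.1) | 7 × 18/24 = 5.25 | 35.25 | 6.75 to 34.75 |
| 5-day cycle as I.6.1 describes it, 12 h spacing | 9 × 12/24 = 4.5 | 34.5 | 7.5 to 35.5 |
| 10 doses at 18 h spacing | 9 × 18/24 = 6.75 | 36.75 | 5.25 to 33.25 |
| Stopped after the first dose of a cycle | Day 0 | Day 30 | 12 to 40 |

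The final leukapheresis is outside the window in every row. The 5-day row is there only because I.6.1 disagrees with the 4-day cycle stated elsewhere; those passages need reconciling, but the result does not depend on which stands.

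**Baseline leukapheresis**
- The procedure comes 28 to 56 days before the first dose, hence before the treatment phase.
- The rule follows the date of death. A death before cycle 1 is missed. A death from the same procedure after dosing has begun is inside the window.

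**What else would catch such a death**

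| Route | Procedure-related death | Drug-related death after about Day 33, still on study |
|---|---|---|
| 3-day SMC notice (H.3.2) | Missed, as set out above | Missed |
| Expedited SMC review and enrolment pause (G, I.3) | Not triggered | Triggered |
| IRB report (H.3.3) | Within 7 calendar days | Within 7 calendar days |
| Report to SMC and FDA (H.3.9) | Yes, no stated deadline | Yes, no stated deadline |

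**A conflict on the time of the final sample.** C.2.1 sets the primary comparison at two weeks after the last rIL-2, about Day 3 + 14 = Day 17, which lies inside the window. D.2.10 schedules the leukapheresis that supplies the sample at Day 42 to 70. The two sections must be reconciled.

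**The case against.** The strongest reply is that this is a drafting mismatch in one rule of a study of at most 20 participants. It affects no endpoint or analysis, the event is unlikely, and other reporting routes exist. Much of that stands, and it rules out three stronger readings that a reader might infer.

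- *Both leukaphereses are wholly outside the rule.* Not so. The window is tied to the date of death, so a late death from the baseline procedure is covered once cycle 1 has started.
- *A procedure-related death would go unreported.* Not so. H.3.3 takes it to the IRB within 7 calendar days, and H.3.9 takes it to the SMC and FDA whatever its cause. H.3.9 even repeats the reporting-day definition for SMC reports, though without a day count.
- *Drug-related deaths after about Day 33 escape the SMC.* Not so. G and I.3 cover any treatment-related death on study, with no 30-day limit, so only the 3-day notice is lost.

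It can also be said that *treatment phase* might mean the whole study, which would close the gap. The documents do not define it. But the added clause on 30 days after the last dose has a purpose only if the phase ends with dosing, and C.5.2 uses the same words for the dosing part of a cycle. Finally, the Manual of Operations and the DAIDS EAE Manual may set further SMC timings; neither is available here, so that cannot be excluded. None of this makes H.3.2 as written cover the procedure-related deaths that it says it covers.

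**Conclusion.** The point holds as a gap between the stated scope of H.3.2 and its window. Any death from the final leukapheresis is missed, because the procedure falls 9 to 37 days after the window closes (at least 5.25 days in the least favourable dosing case). Any death from the baseline leukapheresis in the 28 to 56 days before cycle 1 is missed as well. Because the death triggers in G and I.3 are limited to study treatment, these deaths carry no timed SMC notice, no expedited SMC review and no enrolment pause.

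This rests on two assumptions: *treatment phase* runs from first to last dose, and visits keep to their windows. D.2.12 allows visits a few days off-window, but in the standard case the final visit would have to be 9 days early to fall on Day 33. The gap concerns speed and automatic action only. It is worth correcting because the correction is easy, and no result of the trial depends on it.

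**What to change.** 1. In H.3.2, let the window run from the baseline leukapheresis through the end-of-study visit, or until 30 days after the last study drug dose or the final leukapheresis, whichever is later. State that the D.2.11 immunogenicity follow-up visits do not extend it; otherwise the 3-day duty could run through up to 12 months of antibody follow-up plus 30 days.
2. Name the baseline leukapheresis explicitly as the start. A bare cross-reference to H.3.8 may not be enough, because H.3.8 starts at enrolment and D.3.4.4 lists the leukapheresis visit and entry as separate occasions.
3. In G and I.3, extend the death trigger to deaths related to study treatment or to a study procedure.
4. Reconcile C.2.1 with D.2.10 on when the final sample is taken.

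The cost is a few sentences at the next amendment. For a participant who completes all cycles, the 3-day duty would start 28 to 56 days earlier and end 39 to 67 days later (42 + 30 = Day 72 and 70 + 30 = Day 100, each less Day 33). Enrolment might also be paused after a procedure-related death, which the present text does not require.

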The SMC will review accrual, toxicity summaries, off-treatment and off-study rates, and reasons broken down by study arms. Meetings of the SMC are described above. The SMC will be asked to consider the following regarding safety events: the grade of the event, the time to resolution (if any), and the site clinician's judgment of the relationship to treatment. The first interim safety review by the SMC is planned 3 months after the first subject enrolls and approximately every 3 months thereafter, but expedited reviews will occur whenever the threshold for temporary enrollment discontinuation is reached. Criteria for temporary enrollment discontinuation and expedited SMC review are:

- Three or more participants have experienced a grade 3 AE that is deemed possibly, probably, or definitely related to study treatment
- Two or more participants have experienced a grade 4 AE that is deemed possibly, probably, or definitely related to study treatment
- Any death occurs on study that is deemed possibly, probably, or definitely related to study treatment

The SMC will review the events whenever any of the criteria above is met, and recommend, based on the results of the review, whether the study can proceed as planned, proceed with modifications, or be discontinued.

I.4. Human Subjects Involvement, Characteristics, and Design

Up to 20 participants will be enrolled in the clinical trial. Potential participants will be recruited primarily from the Special Immunology Unit, the HIV clinic of University Hospitals Cleveland Medical Center, although recruitment from other area hospitals through direct outreach and targeted advertisement is also possible. Characteristics of the study population, inclusion/exclusion criteria, and planned study procedures are described in the clinical protocol. No vulnerable populations will be included in these studies.

I.5. Sources of Materials

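### Read literally, the I.3 pause rule misses one pattern, two grade 3 participants and one grade 4, although three grade 3 participants trigger it

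*Combined protocol and SAP*

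**What the plan says.** Section I.3 (Study Discontinuation) lists three criteria for temporarily stopping enrolment and for expedited SMC review:

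- The first concerns grade 3 events and needs three people: "Three or more participants have experienced a grade 3 AE that is deemed possibly, probably, or definitely related to study treatment"
- The second concerns grade 4 events and needs two people: "Two or more participants have experienced a grade 4 AE that is deemed possibly, probably, or definitely related to study treatment"
- The third concerns deaths, where one is enough: "Any death occurs on study that is deemed possibly, probably, or definitely related to study treatment"

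As for the consequence, "expedited reviews will occur whenever the threshold for temporary enrollment discontinuation is reached". The criteria are alternatives, each judged separately: "The SMC will review the events whenever any of the criteria above is met". No sentence pools grades, and none says how a participant with related events of more than one grade is counted. Section I.4 sets the size: "Up to 20 participants will be enrolled in the clinical trial".

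Three other places bear on the point.

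- Section G (Safety Monitoring) gives its own pause rule. It repeats the grade 4 and death criteria, has no grade 3 criterion, and pauses enrolment when either of those two is met.
- Scheduled SMC review runs beside the triggers. I.3 says "The first interim safety review by the SMC is planned 3 months after the first subject enrolls and approximately every 3 months thereafter". Section G instead has reports reviewed "during regularly scheduled conference calls every 6 months" and lets the investigators and SMC chair forgo the call.
- H.3.9 sends AEs of grade 3 and above to the SMC and FDA.

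**The concern.** The thresholds fall from three participants to two to one as severity rises, so one expects a worse set of events never to be less likely to trigger. The first criterion, however, names grade 3 alone. Where the protocol means a grade and everything above it, it says so: I.3 has the SMC monitor events of grade ≥ 2, F.1 refers to hypersensitivity of grade ≥ 3, and H.3.9 refers to grade 3 and above. Against that usage, the plain reading of the first criterion is exactly grade 3.

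On that reading, replacing one of three grade 3 events by a grade 4 event can switch the trigger off. At stake are the automatic pause in enrolment and the speed of the SMC's review, in a trial of at most 20 people. Grade 4 events are not a remote possibility for this agent: Section A.4 reports a hazard ratio of 1.23 (P=0.003) for grade 4 clinical events on rIL-2 in ESPRIT. That figure does not supply a rate of related events for this trial.

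**Working it through.** The plan states no trigger probability or other operating characteristic for the pause rule, so there is no figure to reproduce. The finding rests on enumeration; the probabilities only illustrate its size.

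**Set-up.** Let a be the number of participants whose worst related AE is grade 3, and b the number whose worst is grade 4. Assume no related death, and at first assume that no grade 4 participant also had a separate related grade 3 AE.

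- I.3 as written triggers if a ≥ 3 or b ≥ 2.
- I.3 with grade 3 or higher triggers if a + b ≥ 3 or b ≥ 2.
- Section G triggers if b ≥ 2.

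**Three affected participants.**

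| a (grade 3) | b (grade 4) | I.3 as written | I.3, grade 3 or higher | Section G |
|---|---|---|---|---|
| 3 | 0 | triggers | triggers | silent |
| 2 | 1 | **silent** | triggers | silent |
| 1 | 2 | triggers | triggers | triggers |
| 0 | 3 | triggers | triggers | triggers |

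**All other splits.** I.3 as written is silent only when a ≤ 2 and b ≤ 1, so a + b is at most 3. Within that set the inclusive wording triggers only when a + b = 3, that is, at a = 2, b = 1. Exactly one split changes, and any four participants with related grade 3 or 4 events always trigger.

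**Overlap.** The criterion counts participants who have had a grade 3 event; it does not class people by worst grade. If the grade 4 participant also had a separate related grade 3 AE, the grade 3 count is 3 and the rule triggers.

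**Probability of ending the trial in the silent pattern.** With n = 20 independent participants and per-participant probabilities p3 and p4 of worst related grade 3 and 4:

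P(2, 1) = 20!/(2! 1! 17!) × p3² × p4 × (1 − p3 − p4)^17 = 3420 × p3² × p4 × (1 − p3 − p4)^17

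For p3 = 10% and p4 = 5%: 3420 × 0.01 × 0.05 × 0.85^17 = 0.108. All rates below are assumptions; differences are taken before rounding.

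| p3 / p4 (assumed) | I.3 as written triggers | I.3, grade 3 or higher | Difference = P(2, 1) | Section G triggers |
|---|---|---|---|---|
| 5% / 2% | 13.2% | 18.2% | 5.0 points | 6.0% |
| 10% / 2% | 36.7% | 44.4% | 7.8 points | 6.0% |
| 10% / 5% | 51.3% | 62.1% | 10.8 points | 26.4% |
| 15% / 5% | 71.6% | 80.2% | 8.7 points | 26.4% |
| 20% / 5% | 86.0% | 91.1% | 5.1 points | 26.4% |
| 30% / 5% | 97.8% | 98.8% | 1.0 point | 26.4% |

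At 2% / 1% the same formula gives 3420 × 0.0004 × 0.01 × 0.97^17 = 0.8%. The range over the rates tried is therefore about 1 to 11%.

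**Effect of overlap.** If a share r of grade 4 participants also had a separate related grade 3 AE, P(2, 1) is multiplied by (1 − r). At an illustrative r = 0.5, 10.8% becomes 5.4%. The documents give no r, so each tabulated difference is an upper bound for its rate pair.

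**Section G.** At 10% / 5%, the chance of a trigger is 51.3% under I.3 as written and 26.4% under G, a difference of 24.9 points. The conflict between the sections is larger than the gap inside I.3.

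**The case against.** The strongest reply is that the gap is narrow and other safeguards cover it. Much of this stands. H.3.9 sends grade 3 and higher events to the SMC, scheduled reviews continue, Section G has investigators review every AE of grade 2 or above in real time, and E.2.2 applies dose-adjustment guidelines to grade 3 or 4 AEs unless there is compelling evidence against causation. The whole-trial probability also includes patterns completed after the last enrolment, when a pause has no effect. But none of these safeguards pauses enrolment automatically, and the scheduled interval is itself unsettled between three and six months.

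A second reply is that the authors meant grade 3 to include grade 4. They may have, since no passage states the intent either way. The protocol's explicit inclusive wording elsewhere makes the literal reading fair, and if the inclusive meaning was intended the edit only records it.

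A reader might infer more than the documents support:

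- That a participant with a grade 4 event never counts towards the three. Such a participant does count if there was also a separate related grade 3 AE.
- That severe toxicity in three participants generally goes unreviewed. Three of the four splits trigger, and scheduled review covers the fourth.
- That the conditional risk is the trial's risk. If q is the share of severe related cases whose worst grade is 4, the third case leaves the rule silent with probability 3q(1 − q)², which is 24% at q = 0.10 and 38% at q = 0.20. This presupposes that three such cases have occurred.

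**Conclusion.** The concern holds as a narrow defect of wording. Read literally, the I.3 triggers are non-monotone in one configuration: two participants with worst related grade 3 and one with worst related grade 4 meet no criterion, although three with grade 3 do. This needs only the text and the enumeration. The loss is the automatic pause and the expedited timing, until a fourth participant has a related grade 3 or 4 AE, the grade 4 participant has a separate related grade 3 AE, or another criterion is met.

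The size, about 1 to 11% for ending the trial in this pattern, rests on assumed rates, 20 independent participants, no related death and no overlap between grades. It is worth correcting because the edit is small and the present result is inverted. It does not show that safety oversight as a whole fails.

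**What to change.** In the first I.3 criterion, insert *or higher* after grade 3, so that participants with related grade 4 events count towards the three. Leave the other two I.3 criteria unchanged. This alters exactly one outcome, from silent to triggered.

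Make the edit together with a reconciliation of I.3 and Section G, so that one consistent pause rule applies. Corrected alone, I.3 would still conflict with a section that has no grade 3 criterion; copied into G uncorrected, it would carry the gap over. The three- and six-month review intervals should be reconciled in the same amendment.

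The cost is two words in I.3, the matching text in G, and an occasional earlier SMC review. On the assumed rates above, the chance of a trigger over the whole trial rises by at most about 11 percentage points.
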